5.5.10 Withdrawal of consent

Patients may voluntarily withdraw consent to participate in the study for any reason at any time.

Withdrawal of consent occurs only when a patient does not want to participate in the study anymore and does not want any further visits or assessments and does not want any further study related contacts and does not allow analysis of already obtained biological material.

If a patient withdraws consent, the investigator should make every effort to determine the primary reason for this decision and record this information. Treatment with LCZ696 must be

discontinued and no further assessments conducted. All biological material that has not been analyzed at the time of withdrawal must not be used. Further attempts to contact the patient are not allowed unless safety findings require communication or follow-up.

5.5.11 Loss to follow-up

For patients whose status is unclear because they fail to appear for study visits without stating an intention to withdraw, the investigator should show "due diligence" by contacting the patient, family or family physician as agreed in the informed consent and by documenting in the source documents steps taken to contact the patient, e.g. dates of telephone calls, registered letters, etc. A patient should not be formally considered lost to follow-up until his/her scheduled end of study visit would have occurred.

5.5.12 Emergency breaking of assigned treatment code

This is an open-label study therefore emergency breaking of treatment assignment is not applicable.

5.5.13 Study completion and post-study treatment

Patients who do not fulfill the eligibility criteria should not be enrolled in the study and only baseline characteristics, demographic information and the Screening Log entry should be completed on the eCRF.

When a patient has completed all scheduled study assessments, the investigator must call the IRT within 3 days to record the patient's completion in the IRT. At the EOS visit (Visit 9) patients will be asked to return all remaining LCZ696.

5.5.14 Early study termination

The study can be terminated at any time for any reason by Novartis. Should this be necessary, the patient should be seen as soon as possible and treated for a prematurely withdrawn patient. The investigator may be informed of additional procedures to be followed in order to ensure that adequate consideration is given to the protection of the patient's interests. The investigator will be responsible for informing the Institutional Review Board/Independent Ethics Committee (IRBs/IECs) of the early termination of the trial.

6 Visit schedule and assessments

Following start of LCZ696 treatment (at Visit 1, or at the time of successfully complete the rescreening visits), initial visits up to the visit at 3 months (Visit 4) are set a relatively short interval. The subsequent visits will occur at intervals of 6 months beginning at Visit 6.

Visits 2 should be conducted between 1-to-2 weeks after starting treatment with LCZ696. Visit 3 should be conducted between 2-to-4 weeks and at least 1 week after Visit 2.

Visits 4 through 9 within +/- 7 days of the designated calendar day according to Table 6-1 or as close to it as possible. Specific circumstances surrounding missed or rescheduled visits

must be discussed with the study monitor. Missed or rescheduled visits SHOULD NOT LEAD automatically to patient discontinuation.

Patients should take their scheduled dose of LCZ696 in the morning of their study visits. Patients are not required to fast overnight on the day prior to or the day of the study visit.

The Assessment Schedule ([Table 6-1](#)) lists the assessments to be conducted at each of the study visits (indicated with an “x”).

For patients, who discontinue LCZ696, the discontinuation visit will be Visit 9 (EOS). Enrolled patients who withdraw from the study for any reason, should be scheduled for a visit as soon as possible, at which time all of the assessments listed for Visit 9 (EOS) will be performed. At this final visit all dispensed medication supplies should be reconciled and the Adverse Events and Heart Failure Medications updated on their respective CRFs.

All data obtained from the assessments listed in [Table 6-1](#) must be supported in the patient’s source documentation. The table indicates which data are entered into the CRF from the source data (D), remain in the source documents only (S) or are loaded into the database from separate source documents, i.e. outside vendors (DS). Assessments that generate data for database entry and which are recorded on CRFs are listed using the CRF name.

Table 6-1 Assessment schedule

Epoch		Epoch I Screening	Epoch II Open-label Treatment							
			101	102	103	104	105	106	107	199
Database visit numbering		1	2	3	4	5	6	7	8	9 ² EOS and ITD
Visit ¹		1 *	2	3	4	5	6	7	8	9 ² EOS and ITD
Time	Category	0	1-2 w after start dose	2-4 w	3 m §	6 m §	12 m §	18 m §	24 m	30 m §
Pregnancy test (urine dipstick) ⁶	S	X				X	X	X	X	
Pregnancy test (serum) ⁶	S	X								X
Prior/Concomitant heart failure medications	D/S	X	X	X	X	X	X	X	X	
Adverse events	D/S		X	X	X	X	X	X	X	
Dispense study medications	D/S	X	X	X	X	X	X	X	X	
Drug accountability	S		X	X	X	X	X	X	X	

EOS = end of study; ITD = investigational treatment discontinuation; D = assessment to be recorded on clinical data base; S = assessment to be recorded in source documentation; DS = data transferred from vendor

[§] Within +/- 7 days of the designated calendar day

¹ Unscheduled visits may occur if a safety issue develops

² if a patient fails screening to qualify for the study at Visit 1, s/he may repeat Visit 1 up to two times in order to participate in the study.

³ Visit 9 (End of Study visit) will be completed at approximately 30 months or if the patient permanently discontinues LCZ696 or withdraws early from the study between Visit 1 and Visit 8 or when marketing authorizations are obtained and the product becomes commercially available in the patient's country.

⁴ IRT will be used to enroll patients into the study, dispense open-label medication, track visit dates and record completion or early withdrawal from the trial.

⁵ Height will be measured at Visit 1 only.

⁶ Abbreviated laboratory assessments (performed locally) include serum sodium, potassium and creatinine measured at Visits 2, 3, 4, 7 and 9. At Visits 5, 6 and 8 local labs will include serum sodium, potassium, creatinine, ALT, AST, alkaline phosphatase and total bilirubin.

⁷ Pregnancy testing performed in women of child-bearing potential only, see Section 6.5.6.

⁷ Laboratory values obtained from a sample collected either on the day of Visit 1, or within the last 5 days from Visit 1

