6.3 Treatment exposure and compliance

Dosing information for study medication will be collected on corresponding Dosage Administration Record eCRFs. Compliance will be assessed by the investigator and/or study personnel at each visit using pill counts and information provided by the patient. This information should be captured in the source document at each visit. All investigational treatment dispensed and returned must be recorded in the Drug Accountability Log.

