7.1 Adverse events

All Adverse events reported will be recorded in the e-CRFs regardless of seriousness, causality, or actions (including angioedema-like events). An AE is any untoward medical occurrence (i.e., any unfavorable and unintended sign [including abnormal laboratory

findings], symptom or disease) in a subject or clinical investigation subject *after providing written informed consent* for participation in the study. Therefore, an AE may or may not be temporally or causally associated with the use of a medicinal (investigational) product.

The occurrence of adverse events should be sought by non-directive questioning of the patient at each visit during the study. Adverse events also may be detected when they are volunteered by the patient during or between visits or through physical examination, laboratory tests, or other assessments.

Abnormal laboratory values or test results constitute adverse events only if they fulfill at least one of the following criteria:

- they induce clinical signs or symptoms,
- they are considered clinically significant,
- they require therapy.

Clinically significant abnormal laboratory values or test results should be identified through a review of values outside of normal ranges/clinically notable ranges, significant changes from baseline or the previous visit, or values which are considered to be non-typical in patients with the underlying disease. Investigators have the responsibility of managing the safety of individual patients and identifying adverse events. Alert ranges for labs and other test abnormalities are included in Appendix 1.

Adverse events should be recorded in the Adverse Events CRF under the signs, symptoms or diagnosis associated with them accompanied by the following information.

- the severity grade
 - mild: usually transient in nature and generally not interfering with normal activities
 - moderate: sufficiently discomforting to interfere with normal activities
 - severe: prevents normal activities
- its relationship to the investigational treatment (no/yes)
- its duration (start and end dates) or if the event is ongoing an outcome of not recovered/not resolved should be reported.
- whether it constitutes an SAE
- action taken regarding investigational treatment
- whether other medication or therapies have been taken (concomitant medication/non-drug therapy)

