9.7 Sample size calculation

All surviving patients randomized in PARADIGM-HF can be considered for eligibility in this open-label study (CLCZ6962317). It is estimated that 5,000 patients (about 59% of the core study population and approximately 72% of surviving patients) will meet the eligibility criteria and be enrolled into this open-label trial; however, since there is only one treatment arm in the study and treatment-related statistical comparisons are not planned, a specific sample size for the study is not required.

10 Ethical considerations

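### As extracted, Table 6-1 marks no adverse-event, heart-failure-medication or drug-accountability collection at Visit 9, which contradicts the protocol text and risks under-collection at the final visit

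*Protocol*

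**What the plan says.** Section 6 (Visit schedule and assessments) makes Table 6-1 the operative list: the table "lists the assessments to be conducted at each of the study visits (indicated with an “x". It also says the table shows which data go into the CRF. Patients who stop LCZ696 or withdraw are sent to Visit 9 for the assessments listed there, and the next sentence reads: "At this final visit all dispensed medication supplies should be reconciled and the Adverse Events and Heart Failure Medications updated on their respective CRFs".

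In Table 6-1, as extracted:
- the adverse-event row, "Adverse events D/S X X X X X X X", has seven marks, at Visits 2 to 8;
- the row "Prior/Concomitant heart failure medications" has eight marks, at Visits 1 to 8;
- the drug-accountability row has seven marks, at Visits 2 to 8.

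All three are blank at Visit 9 (database visit 199).

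The text elsewhere reads differently:
- Section 7.1: "The occurrence of adverse events should be sought by non-directive questioning of the patient at each visit during the study".
- Section 6.3: "Compliance will be assessed by the investigator and/or study personnel at each visit using pill counts and information provided by the patient".
- Section 5.5.13: "At the EOS visit (Visit 9) patients will be asked to return all remaining LCZ696".

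**The concern.** The frequency of adverse events is the primary assessment (protocol Section 9.4; SAP Section 9.7.1.6.1). Under Section 5.5.9, permanent discontinuation is withdrawal from the study: there is one final visit and then no assessments except follow-up of an earlier event. For those patients Visit 9 is the last scheduled occasion for asking about events.

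Adverse events and heart failure medications are database items in Table 6-1, so a blank there could carry over into the eCRF build for visit 199. One listed category, events of special interest that lead to permanent discontinuation in patients who start an ACEI or ARB, needs both the event and the medication start.

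Laboratory values are not entered in the clinical database (Section 8.3). A potassium or creatinine abnormality at Visit 9 therefore reaches the analysis only if it is recorded as an adverse event.

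**Working it through.** No power or precision figure bears on this point. The study has one arm, and Section 9.7 says that "a specific sample size for the study is not required". The check compares the table with the text and then reads the visit calendar.

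**1. Could the blanks be a column shift?** Rows that the text also specifies were compared with it.

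| Row | Table 6-1 | Text |
|---|---|---|
| Urine pregnancy test | Visits 1, 5, 6, 7, 8 | same (Section 6.5.6) |
| Serum pregnancy test | Visits 1, 9 | same (Section 6.5.6) |
| Dispensing | Visits 1–8, none at 9 | same (Section 5.5.4) |

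The Visit 9 column was read and does carry a mark, so a shift of whole columns is unlikely. A mark lost from a single cell is not excluded.

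**2. What the text asks for at Visit 9.**

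| Item | Table 6-1 | Patients who discontinue or withdraw | Patients who complete |
|---|---|---|---|
| Adverse events | blank | Sections 6, 7.1, 6.5.1, 6.5.4 | Sections 7.1, 6.5.1, 6.5.4 |
| Heart failure medications | blank | Section 6; Section 9.3 (ACEI/ARB); Section 5.5.7 (no visit named) | Section 5.5.7 only (no visit named) |
| Drug accountability | blank | Sections 6, 6.3, 5.5.13, 5.5.3.1 | Sections 6.3, 5.5.13, 5.5.3.1 |

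Only Section 6 names all three items, and its sentence sits with the instructions for discontinuation and withdrawal. The one cell with no scheduled collection in the text is heart failure medications in completers.

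**3. Length of the exposed interval.** Scheduled visits from Visit 4 on fall at 3, 6, 12, 18, 24 and 30 months. Exposed share = (time of Visit 9 − last marked visit) / time of Visit 9.
- Full length: (30 − 24)/30 = 6/30 = 20%.
- 24 months (German maximum, Section 3.3): (24 − 18)/24 = 25%.
- 20 months (UK maximum): (20 − 18)/20 = 10%.
- 12 months (Danish duration): (12 − 6)/12 = 50%.

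The last three assume that Visit 9 replaces any routine visit due at that time. They apply to the first patient enrolled in the country, because Section 3.3 counts from that date; later patients have shorter follow-up. On the calendar the gap is at most 6 months, apart from the ±7-day windows, and is smaller for a patient who stops between visits.

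**4. Effect of marking Visit 9.** Adverse events and drug accountability go from 7 marked visits to 8, and heart failure medications from 8 to 9. Months 24 to 30 of a full-length patient are then covered.

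**The case against.** The strongest case against is that this is a clerical mismatch in a damaged table, with the data secured elsewhere.

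- **The table.** As extracted it has no rows for physical examination, vital signs, weight or laboratory tests, and its footnote markers are displaced. The blanks may not be in the original. This stands as a caveat, and the page must be checked first.
- **Serious events.** Section 7.2.2 requires reporting until 30 days after the last dose, whatever the visit schedule. This stands.
- **Other events at Visit 9.** Section 6.5.1 requires an examination through Visit 9 and entry of findings that meet the adverse-event definition. Section 6.5.4 does the same for qualifying laboratory abnormalities. Section 7.1 has all reported events recorded and counts those volunteered between visits. This stands, and leaves mainly non-serious events that emerge only on questioning.
- **ACEI or ARB started at discontinuation.** Section 9.3 requires it on the eCRF, and Section 5.5.7 requires all concomitant heart failure medications to be listed. This stands as a requirement, although neither section assigns a visit.
- **Patients who stop.** They have the most explicit instruction, in Section 6. This also stands. It moves the heart-failure-medication gap to completers.

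A reader might infer that every patient's last interval of events is dropped, and might put a figure on it. Suppose a constant rate and an annual incidence of 20%. Cumulative incidence at 30 months is 1 − 0.8^2.5 = 42.8%, against 1 − 0.8^2 = 36.0% at 24 months, a gap of 6.8 points. At 10% a year it is 23.2% against 19.0%, a gap of 4.2 points. The arithmetic is right, but neither incidence is in the documents. The result also needs every site to ignore Sections 6, 6.5.1, 6.5.4 and 7.1, and no patient to volunteer an event. These are hypothetical upper bounds, not estimates of bias.

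**Conclusion.** The contradiction holds, provided the blanks are in the original table. Table 6-1 conflicts with Section 6 on all three items for patients who discontinue or withdraw, with Section 7.1 on adverse events, and with Sections 6.3 and 5.5.13 on drug accountability. It sits in the operative schedule for the primary data, so it is more than a typographical matter.

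The consequence is a risk of under-collection that depends on sites or the eCRF build following the table over the text. It affects non-serious events found only by questioning since the last routine visit, at most about 6 months, and heart failure medication updates in patients who reach Visit 9 at month 30 or at country closure. The documents do not support a claim that serious events or the ACEI/ARB starts at discontinuation will be lost, and they give no basis for a percentage-point bias.

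**What to change.** 1. Confirm the three blank cells on the original page of Table 6-1.
2. If they are blank there, mark adverse events, prior/concomitant heart failure medications and drug accountability at Visit 9.
3. Reword the Section 6 sentence so that the reconciliation and the two updates apply to every Visit 9, including month-30 and country-closure visits.
4. Check that the visit-199 eCRF contains the adverse-event and heart failure medication forms, and that drug accountability is in the source worksheets for that visit.

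This costs three table cells, one sentence and a database check. An administrative amendment would be enough: Amendment 2 was of that type and corrected Figure 3-1 to agree with the text. No visit, procedure or treatment rule changes.

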6.1 Information to be collected on screening visit (Visit 1)

Please refer to [Table 6-1](#) Assessment Table for the information to be collected during the Screening visit. If a patient is not eligible for enrollment, the investigator may consider re-screening the patient at a later time if he/she believes that the patient's condition has changed and may potentially be eligible. In this case, a completely **new patient number will be allocated to the subject** and he/she will need to re-perform all Visit 1 assessments. A patient may be re-screened for enrollment in this protocol up to two additional times with a minimum of 2 weeks between re-screening visits. The patient must provide new written informed consent before each time they are to be re-screened.

For these patients that are considered screening failures only baseline characteristics, demographic information, and the Screening Log entry with the reason for screen failure should be completed on the eCRF.

6.2 Patient demographics/other baseline characteristics

Patient demographic and baseline characteristic data will be collected including: year of birth, age, sex, race and ethnicity, as well as the Identification Number (ID No.) the subject was formerly assigned in the PARADIGM-HF study (CLCZ696B2314). Relevant medical history/current medical condition data includes data until the start of study drug. When possible, diagnoses and not symptoms will be recorded. HF medications will be recorded on the prior/concomitant Heart Failure Medications eCRF.

6.3 Treatment exposure and compliance

Dosing information for study medication will be collected on corresponding Dosage Administration Record eCRFs. Compliance will be assessed by the investigator and/or study personnel at each visit using pill counts and information provided by the patient. This information should be captured in the source document at each visit. All investigational treatment dispensed and returned must be recorded in the Drug Accountability Log.

6.4 Efficacy

Efficacy variables will not be assessed in this study.

6.5 Safety

The Sponsor may request additional information on specific adverse events or laboratory events of interest and may make requests to perform additional diagnostic tests to further assess the safety profile of LCZ696. Such information may include diagnostic procedure reports, discharge summaries, autopsy reports, and other relevant information that may help in assessing the reported adverse event. All additional information will be de-identified prior to collection by Novartis or its agents.

6.5.1 Physical examination

A physical examination will be performed at every visit through the End of Study visit (Visit 9). It will include the examination of general appearance, skin, neck (including thyroid), eyes, ears, nose, throat, lungs, heart, abdomen, back, lymph nodes, extremities, vascular and neurological. If indicated based on medical history and/or symptoms, rectal, external genitalia, breast, and pelvic exams will be performed.

Information for all physical examinations must be included in the source documentation at the study site. Significant findings that are present prior to signing informed consent must be included in the Medical History part of the eCRF. Significant findings made after signing the informed consent which meet the definition of an Adverse Event must be recorded in the Adverse Event section of the eCRF.

6.5.2 Vital signs

Vital signs will be assessed at every visit. This will include SBP/DBP and pulse measurements. SBP/DBP will be measured by using a standard sphygmomanometer with an appropriate size cuff and the non-dominant arm in the sitting position after 5 minutes of rest.

6.5.3 Height and weight

Height in centimeters (cm) will be measured at Visit 1.

Body weight (to the nearest 0.1 kilogram [kg] in indoor clothing without shoes) will be measured every visit through the End of Study visit (Visit 9).

6.5.4 Laboratory evaluations

Laboratory samples will be analyzed locally. Values outside the normal ranges and notable values should be flagged on the report. It is the responsibility of the investigator to review all laboratory results and make an assessment of whether an abnormal or notable value is clinically significant, whether additional evaluations should be performed as judged appropriate, and whether the patient may continue in the trial. Sample collection should be conducted according to the standards and requirements of the local laboratory.

- Laboratory values that exceed the boundaries of a notable laboratory abnormality (refer to [Appendix 1](#)) must be commented on by the investigator in the source documents and additional laboratory evaluations should be performed, as judged appropriate by the investigator.
- If the laboratory abnormality induces clinical signs or symptoms, or requires therapeutic intervention, and satisfies the criteria defined in [Section 7.1](#), then the diagnosis or medical condition must be entered on the AEs page of the patient's eCRF and any treatment necessary should be documented. If the laboratory abnormality is the primary reason for an unforeseen hospitalization or otherwise fulfills the seriousness category of an AE, then the procedure for rapid notification of SAEs must be followed.
- Likewise, if the laboratory abnormality leads to discontinuation of the study drug, the patient must be followed until the abnormality resolves or until it is judged to be permanent. This investigation may include continued monitoring by repeat laboratory

testing or by performing additional laboratory tests as deemed necessary by the investigator or the Sponsor's medical monitor.

Clinically notable laboratory findings are defined in [Appendix 1](#).

Full laboratory clinical chemistry ([Table 6-2](#)) will be performed locally at Visit 1 and abbreviated laboratory evaluations (sodium, potassium, creatinine) will be performed locally at Visits 2, 3, 4, 7 and 9. At Visits 5, 6 and 8 local labs will include sodium, potassium, creatinine, ALT, AST, alkaline phosphatase and total bilirubin.

Full laboratory tests will include the following:

Table 6-2 Full laboratory evaluations

Biochemistry
Sodium
Potassium
BUN
Creatinine
Total bilirubin
AST
ALT
γ GT
Alkaline phosphatase
Creatine phosphokinase (CPK)
Uric acid
Total protein
Albumin

